3.3 Prior, Concomitant, and Subsequent Medications/Procedures

Medications will be coded to preferred term and Anatomical Therapeutic Chemical (ATC) class according to World Health Organization (WHO) Drug dictionary.

Prior medications are defined as medications that started prior to the first dose date of study drug. Prior anti-neoplastic therapies will be summarized separately.

Concomitant medications are defined as medications that were taken at any time on treatment (i.e. from the date of the first dose of study drug through the date of the last dose of study drug) and will be summarized separately. Concomitant use of CYP3A inhibitors (strong, moderate, and weak) and CYP3A4 inducers will be listed and summarized separately.

3.4 Subsequent Anti-Cancer Treatment

Subsequent anticancer therapies are anti-DLBCL treatments that started after discontinuation of study treatment (i.e. started after the last dose of study drug) will be summarized for the all-treated population by type (e.g. radiotherapy, systemic therapy, bone marrow or stem cell transplant).

3.5 Extent of Exposure to Study Drug

For each study treatment, the number of treatment cycles each subject received will be summarized for the all-treated population. Subjects with any dose interruption or dose reduction due to AEs will be summarized.

Summary tables for ibrutinib, lenalidomide, and rituximab will present duration of treatment, the number of doses received, the total amount of study drug received, the average dose per

Statistical Analysis Plan

PCYC-1123-CA

20APR2020

administration, the relative dose intensity, and subjects with at least 1 dose modification (interruption or reduction) due to AE.

For rituximab, the average dose per administration, relative dose intensity, the number and percentage of subjects with infusion interruption, duration of interruption, and at least 1 dose modification will be summarized.

4 EFFICACY EVALUATIONS

The Response-evaluable population (Phase 1b/2) is the primary analysis population for ORR and the CR rate. The ORR and the CR rate will be calculated for the all-treated population as well. The all-treated population is the primary analysis population for all other efficacy endpoints (i.e. PFS, OS). The analysis of endpoints is presented in Table 4.

The scanned images will be centrally stored for a possible future independent review of overall response. In case PCYC decides to implement an independent review of tumor response data, the overall response as assessed independently will become the primary analysis set for ORR, CR, DOR and PFS, and the previous analyses by investigators' assessments will become a secondary analysis set.

Table 4: Definitions and Analyses for Efficacy Endpoints

Endpoint	Definition	Analysis Method
Phase 1b:		
Secondary Endpoints (for all subtypes of DLBCL):		
ORR	
The ORR is defined as the rate of subjects who achieve either a PR or CR, according to the revised International Working Group Response Criteria for NHL (Cheson 2007), as assessed by the Investigator.
	
ORR and its corresponding exact binomial 2-sided 95% CI, based on the response-evaluable population enrolled in Phase 1b.
 
Sensitivity
 
Analysis based on the all-treated population enrolled in Phase 1b.
 
In addition, waterfall plot for maximum percent reduction in tumor size and time to response will be summarized.

CR rate	
The ORR is defined as the rate of subjects who achieve a CR, according to the revised International Working Group Response Criteria for NHL (Cheson 2007), as assessed by the Investigator.
	The same as for ORR

Statistical Analysis Plan

PCYC-1123-CA

20APR2020

Endpoint	Definition	Analysis Method
Phase 2:		
Primary Endpoint:		
ORR	
The ORR is defined as the rate of subjects who achieve either a PR or CR, according to the revised International Working Group Response Criteria for NHL (Cheson 2014), as assessed by the Investigator.
	
ORR and its corresponding exact binomial 2-sided 95% CI, based on the response-evaluable population enrolled in Phase 2.
 
Sensitivity
 
Analysis based on all-treated population enrolled in Phase 2.
 
In addition, a waterfall plot for maximum percent reduction in tumor size and time to response will be summarized.

Secondary Endpoints:		
CR rate	
The ORR is defined as the rate of subjects who achieve a CR, according to the revised International Working Group Response Criteria for NHL (Cheson 2014), as assessed by the Investigator
	The same as for ORR
DOR	
Time from the date of the first documented response (CR or PR) to the first documented evidence of PD or death from any cause.
 
For subjects who have achieved an overall response but did not die or progress at the time of analysis, DOR will be censored on the date of the last adequate post-baseline disease assessment, or on the date of the first occurrence of response (CR or PR) if there is no disease assessment afterwards.
	
Analysis of DOR will be based on the subjects who have achieved a response (CR or PR) prior to initiation of the next line of anticancer therapy in the all-treated population enrolled in Phase 2. The median DOR and its 2-sided 95% CI will be obtained using the same method described for PFS.
 
Similar analysis for duration of CR, as defined as time from the date of the initial CR to the first documented evidence of PD or death from any cause, will be performed for all treated subjects who have achieved a response of CR prior to initiation of the next line of anticancer therapy in Phase 2.

PFS	
Time from the date of the first dose of study drug to confirmed PD or death from any cause, whichever occurred first.
 
For subjects without disease progression or death, PFS data will
	
Kaplan-Meier method based on the all-treated population by dose level enrolled in Phase 2. The median PFS and its 2-sided 95% CI will be provided. PFS at landmark time points (e.g., 3, 6, 9, 12 months from the first study drug dose date) will also be obtained by the Kaplan-Meier method; 95% CI for the landmark PFS rates will be calculated.

Statistical Analysis Plan

PCYC-1123-CA

20APR2020

Endpoint	Definition	Analysis Method
OS	
be censored at the date of the last tumor assessment.
 
Overall survival (OS) is defined as the time from the date of the first dose of study drug to the date of death due to any cause.
 
For subjects who are not known to have died at or prior to the database lock date, OS data will be censored at the date last known alive. Subjects who withdraw consent prior to study closure will be censored on the date of the consent withdrawal.
	
Kaplan-Meier method based on the all-treated population by dose level enrolled in Phase 2. The median OS and its 2-sided 95% CI will be provided. OS at landmark time points (e.g., 3, 6, 9, 12 months from the first study drug dose date) will also be obtained by the Kaplan-Meier method; 95% CI for the landmark OS rates will be calculated.

Exploratory Analysis:		
Peripheral T/B/NK counts	The absolute cell counts on peripheral T/B/NK	Summary statistics will be calculated for the measured values and for their changes from baseline at each scheduled visit of assessment.
Serum immunoglobulin levels	The serum immunoglobulin levels (IgG, IgM, and IgA)	Summary statistics will be calculated for the measured values and for their changes from baseline at each scheduled visit of assessment.
Efficacy endpoints (DOR, PFS, and OS) by DLBCL subtype per GEP	See definitions above for DOR, PFS, and OS	Subgroup analyses will be performed as defined in Table 3. See analysis methods above for DOR, PFS, and OS.

ABC: Activated B cell-like; CI: confidence interval; CR: complete response; DLBCL: diffuse large B-cell lymphoma; ECOG PS: Eastern Cooperative Oncology Group Performance Status; GCB: germinal center B cell-like; GEP: gene expression profile; IHC: immunohistochemistry; KM: Kaplan-Meier; ORR: overall response rate; OS: overall survival; PD: progressive disease; PFS: progression-free survival; PR: partial response; RP2D: recommended phase 2 dose.

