10.1.1. Response Assessment

Response assessments will be made by the Investigator. Tumor response will be assessed by the Investigator using the revised International Working Group Response Criteria for NHL ([Cheson 2007](#)) for Phase 1b and the revised International Working Group Response Criteria for NHL or Lugano Classification ([Cheson 2014](#)) for Phase 2.

Confirmation of Investigator-assessed responses by an independent review committee (IRC) may be done as a supportive assessment. The method of independent review will be governed by an IRC charter.

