10.3.2. Efficacy Endpoints for Phase 1b

The efficacy endpoints for the Phase 1b of this study are ORR and CR rate. The ORR of Phase 1b and its 95% 2-sided exact confidence interval will be calculated for the response-evaluable population and the all-treated population of Phase 1b. The CR rate of Phase 1b will be analyzed likewise.

10.3.3. Primary Efficacy Endpoint for Phase 2

The primary efficacy endpoint for Phase 2 is the overall response rate (ORR). The ORR is defined as the rate of subjects who achieve either a PR or CR, according to the revised International Working Group Response Criteria for NHL, as assessed by the Investigator (Cheson 2014). The ORR will be calculated for the response-evaluable population of Phase 2. The corresponding 95% 2-sided exact CI will be derived. If the lower bound of the CI around the ORR is greater than or equal to 40%, then the hypothesis that the ORR of the ibrutinib combination treatment is equal to or lower than 40% will be rejected. The ORR will also be calculated for the all-treated population of Phase 2.

10.3.4. Secondary Efficacy Endpoints for Phase 2

The secondary efficacy endpoints for Phase 2 of this study are CR, DOR, PFS and OS.

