10.3.4.1. Complete Response

Complete response rate will be analyzed by the same method used for the analysis of ORR.

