10.3.4.2. Duration of Response

For subjects achieving an overall response as assessed by the Investigator, their DOR as assessed by the Investigator will be calculated to determine durability. Duration of response will be measured from the time by which the measurement criteria are met for CR or PR, whichever is recorded first, until death or the first date by which recurrent or progressive disease is objectively documented (taking as reference for progressive disease the smallest measurements recorded since the treatment started). For subjects without disease progression or death, DOR will be censored at the date of the last tumor assessment.

The distribution (median, its 95% CI and Kaplan-Meier curves) of DOR will be provided using Kaplan-Meier estimates for responders in the all-treated analysis population.

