10.3.4.3. Progression-Free Survival

Progression-free survival will be measured as time from first study drug administration to lymphoma progression or death from any cause. Data for subjects without disease progression or death will be censored at the date of the last tumor assessment.

Progression-free survival will be calculated using assessments by the Investigator. Kaplan-Meier methodology will be used to estimate event-free curves and corresponding quartiles (including the median). The distribution (median, its 95% CI and Kaplan-Meier curves) of PFS will be provided using Kaplan-Meier estimates in the all-treated analysis population.

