1 INTRODUCTION

This statistical analysis plan (SAP) is based on Protocol Amendment 5, dated on 01JUN2016, and is to define key elements including variable definitions, and statistical methods for analysis of data in the evaluation of efficacy and safety of the study PCYC-1123-CA. Analyses of biomarker and pharmacokinetics data will be addressed in separate documents.

Analysis methods specified in this document take precedence over those described in the protocol, should there be any difference.

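### SAP Section 4 makes an optional independent read primary if the sponsor commissions one, with no deadline or result-blind condition; the protocol calls it supportive, and SAP Section 6 does not declare the change.

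*SAP*

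**What the plan says.** **Protocol.** Section 10.1.1 gives response assessment to the investigator and adds: "Confirmation of Investigator-assessed responses by an independent review committee (IRC) may be done as a supportive assessment". It also says "The method of independent review will be governed by an IRC charter". Section 7.3.1 leaves the decision to hold such a review to the sponsor. The endpoint definitions are consistent with this:

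- ORR (10.3.3): "Response Criteria for NHL, as assessed by the Investigator"
- CR (10.3.4.1): "Complete response rate will be analyzed by the same method used for the analysis of ORR"
- DOR (10.3.4.2): "their DOR as assessed by the Investigator will be calculated to determine durability"
- PFS (10.3.4.3): "Progression-free survival will be calculated using assessments by the Investigator"

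**SAP.** Section 4 stores the scans for a possible later independent review. It states that, if the sponsor decides to hold one, "the overall response as assessed independently will become the primary analysis set for ORR, CR, DOR and PFS", while the earlier investigator-based analyses become secondary. Section 1 gives the SAP the last word: "Analysis methods specified in this document take precedence over those described in the protocol, should there be any difference". Section 6, on changes from the protocol's planned analysis, records only the delay of the clinical study report.

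**The concern.** The SAP swaps the roles of the two reads for the primary endpoint and three secondary endpoints, and the swap depends on a later sponsor decision. Once a review is run, its read is primary whatever it shows. The sponsor's freedom is therefore limited to whether and when to commission it. That freedom still matters in an open-label trial with one pass mark: a sponsor who has seen the investigator count can leave a success alone and ask for a second read after a miss.

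Two things are at stake. The first is the stated one-sided error of 0.025, which assumes that the deciding read does not depend on the result. The second is disclosure: someone who relies on SAP Section 6 to learn how the analysis departs from the protocol would not find that the primary assessor can change.

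**Working it through.** **1. The passages side by side**

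| Question | Protocol | SAP |
|---|---|---|
| Primary read for ORR, CR, DOR, PFS | Investigator | Investigator, unless a review is run; then independent |
| Status of an independent review | Supportive (10.1.1) | Primary (Section 4) |
| Who decides to run it | Sponsor (7.3.1) | Sponsor (Section 4) |
| Deadline or result-blind condition | None | None |
| Listed as a change | n/a | Not in Section 6 |

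The switch is also not carried through the SAP. Table 4 still defines ORR and CR by the investigator's assessment. The response-evaluable set in Section 2.1 still requires an adequate assessment by the investigator, so after a switch the responses and the denominator would rest on different readers.

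**2. The plan's own figure.** Inputs from SAP 1.4: n = 49, success at 27 or more responses, null ORR 0.40, alternative 0.60. With X binomial on one fixed read:

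- P(X ≥ 27 | 0.40) = 0.0231, against a stated 0.025
- P(X ≥ 27 | 0.60) = 0.8018, against a stated 80%

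The stated figures hold; 0.025 is a ceiling because the count is discrete. A binding stop at 11/28 changes them only to 0.0230 and 0.800, so the interim is ignored below.

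**3. Two reads of the same 49 subjects.** Let p be the investigator read's true ORR, q the independent read's, and a the probability that the two reads agree on a subject. The documents give neither q nor a, so both are assumptions. The cell probabilities are:

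- respond on both reads: p11 = (a − 1 + p + q)/2
- investigator only: p10 = p − p11
- independent only: p01 = q − p11
- neither: p00 = 1 − p11 − p10 − p01

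Let I and R be the investigator and independent counts. Given I = x, R is the sum of a Bin(x, p11/p) and a Bin(49 − x, p01/(1 − p)) variable. Summing over x from 27 to 49 gives P(both ≥ 27) exactly. If a review is commissioned only after I < 27, then

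P(declared success) = P(I ≥ 27) + P(R ≥ 27) − P(both ≥ 27).

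Example with p = q = 0.40 and a = 0.90: p11 = 0.35, p10 = p01 = 0.05, p00 = 0.55 and P(both ≥ 27) = 0.0101. The error is 0.0231 + 0.0231 − 0.0101 = 0.0361. The chance that a review after a miss turns it into a success is (0.0231 − 0.0101)/(1 − 0.0231) = 0.0133.

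**4. Results, p = 0.40, review only after a miss**

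| Independent read's true ORR | a = 95% | 90% | 85% | 80% |
|---|---|---|---|---|
| 40% | 0.0323 | 0.0361 | 0.0388 | 0.0407 |
| 38% | 0.0255 | 0.0279 | 0.0296 | 0.0309 |
| 36% | 0.0234 | 0.0245 | 0.0255 | 0.0262 |
| Miss turned into success (40% row) | 0.0094 | 0.0133 | 0.0160 | 0.0180 |

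At 40% on both reads, 76% agreement (kappa = (0.76 − 0.52)/(1 − 0.52) = 0.50) gives 0.0419. Wholly unrelated reads, implausible for the same scans, give 1 − (1 − 0.0231)² = 0.0457. These are grid values, not bounds. An independent ORR above 40% is left out because the null is then false for that read.

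**5. Cases without inflation.** With no review, the error is 0.0231. With a review run regardless of the result and q = 0.40, it is P(R ≥ 27) = 0.0231.

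**The case against.** The strongest reply is that the harm is contingent. No document shows that a review was run, and without one the investigator read stays primary and nothing is inflated. That is correct. The error figures need a review that is run because of a miss, on a read whose true ORR is close to 40%.

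The clause also binds the other way. A review run only after an investigator success can overturn it; with both reads at 40% the error is then P(both ≥ 27), or 0.014 to 0.006 for agreement of 95% to 80%. This is correct too, but it is not the route that threatens 0.025, and nothing obliges the sponsor to take it.

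The error argument reaches only ORR, the one endpoint with a hypothesis test. For CR, DOR and PFS the issue is which estimate is labelled primary. That stands.

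The review charter might fix the timing. It is not available, and the protocol says only that it governs the method of review, so the missing condition is established for the protocol and SAP alone.

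A central read can guard against investigator bias in an open-label trial, and the SAP states the rule openly in Section 4 and claims precedence over the protocol. These points defend the independent read as a choice. They do not supply a time at which the choice must be made, and the precedence clause settles which document governs without declaring this change.

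**Conclusion.** The concern holds as stated. The SAP, which governs, reverses the protocol's ranking of the two reads on a sponsor decision that neither document ties to a date or to ignorance of the results, and SAP Section 6 does not record the reversal. This conclusion rests on the text and needs none of the assumed values.

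The effect on the primary test is modest and conditional. The one-sided error moves from 0.023 to between 0.032 and 0.041 only if a review follows a miss, both reads have a true ORR of 40%, agreement is 95% to 80%, and the same 49 subjects count on each read. It stays close to nominal if the independent read is stricter (0.023 to 0.026 at 36%).

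Three things cannot be seen from the documents: which reader produced the 2019 results, whether the clause predates that presentation, and what the charter says about timing. The point should be fixed; it does not show that any result is invalid.

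**What to change.** **Preferred.** Replace the SAP Section 4 sentence with the protocol's rule, for example: *The investigator's assessment is the primary analysis for ORR, CR, DOR and PFS. Any independent review is supportive and is reported beside it with agreement statistics, whatever its result.* This costs one sentence and no new data; agreement statistics are needed only if a review is run. The sponsor gives up the option of promoting the independent read later, but that read stays visible as supportive.

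**Alternative.** If the sponsor wants the independent read as primary, say so in a dated amendment, list it in SAP Section 6 with a statement of which results were known by then, align Table 4, state which read defines the response-evaluable set, and report both reads. This costs the amendment, the Section 6 entry and the central read itself.

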5 SAFETY EVALUATION

Safety data for the all-treated population will be summarized for Phase 1b by the dose for Phase 2, unless otherwise indicated. Table 5 summarizes the safety analyses to be conducted.

Adverse events will be coded in accordance with the Medical Dictionary for Regulatory Activities (MedDRA). Severity of AEs will be graded by the investigator according the NCI Common Terminology Criteria for Adverse Events (NCI-CTCAE) (version 22.1 or higher).

Statistical Analysis Plan

PCYC-1123-CA

20APR2020

In general, the treatment-emergent period is defined as the period from the date of the first dose of study treatment up to 30 days after the date of the last dose of study treatment or the day before initiation of subsequent anticancer therapy, whichever comes first. Treatment-emergent AEs are those events that occur or worsen during the treatment-emergent period or that are related to the study treatment or events with a complete missing onset date but with a resolution date during the treatment phase.

All laboratory values will be converted to and reported as international standard (SI) units. In general, only data from the central laboratory will be summarized and analyzed. Laboratory parameters will be graded using the NCI CTCAE (version 4.03 or higher). Unless otherwise specified, only baseline and post-baseline values collected during the treatment-emergent period will be included in the safety analysis.

Table 5: Summary of Safety Assessments

Assessment Type	Definition	Analysis Methods
AE	TEAEs, SAEs, grade 3 or higher TEAEs, study treatment-related TEAEs, TEAEs as the primary reason for treatment discontinuation, TEAEs leading to treatment discontinuation, TEAEs leading to dose reduction, TEAEs leading to death, protocol-defined events of special interest and other safety observations	Descriptive summary statistics and/or listings
Lab	Worst post-baseline toxicity grade for selected CTCAE gradable hematology and chemistry. Abnormalities in creatinine clearance, uric acid, and liver function.	Descriptive summary statistics and/or listings. For gradable lab results, the worst toxicity grade during the study will be tabulated and the summary of treatment-emergent abnormal laboratory results with 2 or more grade worsening will be provided.
Vital Signs and other Observations Related to Safety	SBP, DBP, heart rate, body temperature, weight, and ECOG PS	The baseline and the change from baseline will be summarized by scheduled visits.
DLT	DLT	Listing

CTCAE= Common Terminology Criteria for Adverse Events; DLT: dose limiting toxicity; ECOG: Eastern Cooperative Oncology Group; TEAE: treatment-emergent adverse event; SAE= serious adverse event; SBP: systolic blood pressure; DBP: diastolic blood pressure

Statistical Analysis Plan

PCYC-1123-CA

20APR2020

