10.3.6. Safety Endpoint

Safety summaries will include tabulations in the form of tables and listings. The frequency (number and percentage) of treatment-emergent AEs will be reported by MedDRA® System Organ Class and Preferred Term. Additional AE summaries will include AE frequency by AE severity and by relationship to study drug.

Adverse events requiring discontinuation of study drug will be summarized separately, both overall and by AE severity and by relationship to study drug.

Clinically significant abnormal laboratory values will be summarized. Laboratory shift tables containing counts and percentages will be prepared by laboratory parameter and time. Summary tables will be prepared for each laboratory parameter. Figures of changes in laboratory parameters over time will be generated.

Safety: Missing or partial start and end dates for AEs and concomitant medications will be imputed according to pre-specified, conservative imputation rules. No other imputation of values for missing data will be performed.

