10.6.1. Adverse Events

Adverse event parameters to be evaluated are the type, incidence, and intensity of AEs; the relationship of AEs to ibrutinib; and the action taken with respect to ibrutinib treatment due to AEs.

The verbatim terms used in the eCRF by the Investigator to identify non-hematological adverse events will be coded using the Medical Dictionary for Regulatory Activities (MedDRA®). Treatment-emergent AEs are those AEs events occurring after the first dose of study drugs and within 30 days following the last dose of study drug; any AE that is considered study drug-related regardless of the start date of the event; or any AE that is present at baseline but worsens after the first administration of study drug in severity or is subsequently considered drug-related by the Investigator. All treatment-emergent AEs will be included in the analysis. For each AE, the percentage of subjects who experience at least 1 occurrence of the given event will be summarized. The number and percent of subjects with treatment-emergent adverse events will be summarized according to intensity ([NCI CTCAE, Version 4.03](#)) and drug relationship as well as categorized by system organ class and preferred term. Summaries, listings, datasets, or subject narratives may be provided, as appropriate, for those subjects who die, who discontinue treatment due to an AE, or who experience a SAE.

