11.1.4. Severity Criteria (Grade 1-5)

Definitions found in the Common Terminology Criteria for Adverse Events version 4.03 ([CTCAE v4.03](#)) will be used for grading the severity (intensity) AEs. The [CTCAE v4.03](#) displays Grades 1 through 5 with unique clinical descriptions of severity for each referenced AE. Should a subject experience any AE not listed in the [CTCAE v4.03](#), the following grading system should be used to assess severity:

- Grade 1 (Mild AE) – experiences which are usually transient, requiring no special treatment, and not interfering with the subject's daily activities

- Grade 2 (Moderate AE) – experiences which introduce some level of inconvenience or concern to the subject, and which may interfere with daily activities, but are usually ameliorated by simple therapeutic measures
- Grade 3 (Severe AE) – experiences which are unacceptable or intolerable, significantly interrupt the subject's usual daily activity, and require systemic drug therapy or other treatment
- Grade 4 (Life-threatening or disabling AE) – experiences which cause the subject to be in imminent danger of death
- Grade 5 (Death related to AE) – experiences which result in subject death

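### The SAP's rule for adverse events with a completely missing onset date counts a not-related, non-worsening event only if it resolved during treatment, so the same event left ongoing is dropped

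*SAP*

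**What the plan says.** **Routes to treatment-emergent status.** SAP section 5 counts "those events that occur or worsen during the treatment-emergent period or that are related to the study treatment", and adds "or events with a complete missing onset date but with a resolution date during the treatment phase". The SAP does not define the treatment phase and gives no imputation rules for adverse event dates.

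**Missing dates in the protocol.** The definition in section 10.6.1 has no clause for a missing onset. Section 10.3.6 covers it in general terms: "Missing or partial start and end dates for AEs and concomitant medications will be imputed according to pre-specified, conservative imputation rules". The rules themselves are not given.

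**Where events are recorded.** Under protocol section 7.1.6, events between consent and first dose go to medical history. Sections 7.1.6 and 11.2.2.1 start adverse event entry in the eCRF at first dose and continue it to 30 days after the last dose.

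**End of the window.** The SAP closes the period at 30 days after the last dose "or the day before initiation of subsequent anticancer therapy, whichever comes first". Protocol section 10.6.1 takes events "occurring after the first dose of study drugs and within 30 days following the last dose of study drug", with no cut at new therapy.

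**Precedence.** The SAP introduction makes the SAP prevail where the two differ. SAP section 6, on changes to the planned analysis, lists only the delayed study report.

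**Grading.** SAP section 5 attaches "version 22.1 or higher" to CTCAE for adverse events, and 4.03 or higher for laboratory values. Protocol section 11.1.4 uses "Common Terminology Criteria for Adverse Events version 4.03".

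**The concern.** A rule for missing onset dates should not look at how the event ended. Here it does. Of two otherwise identical not-related events with no start date, the one that resolved on treatment is tabulated and the one that persisted is not. Because pre-dose events belong in medical history, a blank-onset record on the adverse event form should be presumed to have started after first dose, which makes the exclusion hard to justify.

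Safety and tolerability is a primary objective of Phase 1b and a secondary one of Phase 2. The SAP's Table 5 builds its summaries of treatment-emergent events on this definition, including those of Grade 3 or higher and those leading to discontinuation, dose reduction or death.

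**Working it through.** The plan gives no figure to reproduce, so the check is a comparison of rules on example cases.

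**Assumptions for illustration (not in the documents).** First dose is day 1 and last dose day 100, so the 30-day limit is day 100 + 30 = 130. Where there is new therapy it starts on day 110, so the SAP period ends on the earlier of 130 and 110 − 1 = 109. Conservative imputation is taken to set a missing onset to the first-dose date unless the event ended before it.

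**Two readings of treatment phase.** Narrow: first to last dose, close to protocol section 3.1, where the Treatment Phase ends once permanent discontinuation criteria are met. Wide: the SAP's treatment-emergent period.

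| Case | SAP, narrow | SAP, wide | Protocol with imputation |
|---|---|---|---|
| **Onset missing, not related, no recorded worsening** | | | |
| Resolved day 80 | counted | counted | counted |
| Ongoing, or end date blank | dropped | dropped | counted |
| Resolved day 105 | dropped | counted | counted |
| Resolved day 120, no new therapy | dropped | counted | counted |
| Resolved day 120, new therapy day 110 | dropped | dropped | counted |
| Resolved day 140 | dropped | dropped | counted |
| **Onset missing, other** | | | |
| Related, ongoing | counted | counted | counted |
| Worsening recorded day 60, ongoing | counted | counted | counted |
| **Onset known, not related, no recorded worsening** | | | |
| Onset day 50, ongoing | counted | counted | counted |
| Onset day 115, new therapy day 110, resolved or not | dropped | dropped | counted |

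**What follows.**

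1. The dependence on outcome shows in the first two rows: same event, different ending, different classification. It holds on either reading of treatment phase.
2. On the narrow reading, events that resolve between the last dose and day 130 are lost as well, although they end inside the 30-day window. The wide reading recovers them only up to the end of the SAP period.
3. Related events, and events with recorded worsening in the period, are counted whatever their resolution.
4. The last row is a different mechanism. The cut at new therapy acts on the start date and drops not-related events whether they resolved or not.

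**The case against.** **The protocol's imputation still applies.** Nothing in SAP section 5 withdraws it. If a missing onset is set to first dose, the event occurs in the period and enters by the first route, so the missing-onset clause only adds cases. This does not remove the problem. If missing onsets were imputed to first dose, the clause would be unnecessary; its presence implies that they are left missing. The SAP also states no imputation rule and takes precedence where it differs. What stands is that the protocol's rules are not spelled out, so its treatment of these events is a strong inference and not an express provision.

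**A reader might infer that any missing-onset event counts only if it resolved.** The text does not say that. The three routes are alternatives, and related or worsening events remain in.

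**A reader might infer that the regimen is made to look safer overall.** A net bias is not shown. The missing-onset clause could also admit an event that began before dosing and resolved on treatment. Table 5 lists serious events without a treatment-emergent qualifier, dose-limiting toxicities are listed separately, and overall survival counts every death.

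**A reader might treat the cut at new therapy as an error and put a size on it.** Ending the window there avoids charging the next regimen's toxicity to this one, and protocol section 8.3.19 allows the End-of-Treatment Visit before new treatment starts. If new therapy began on day 7 after the last dose, 23/30 = 77% of the post-dose window would go. But day 7 is an assumption, the documents give no time to next therapy, and a share of days is not a share of events. What stands is that the change is undeclared.

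**A reader might take the CTCAE version as a change of grading scale.** It follows a MedDRA sentence that has no version, so a misplaced number is the likely explanation. No event count turns on it.

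**Conclusion.** The concern holds in a limited form. For events with a completely missing onset, no judged relation to study treatment and no recorded worsening, SAP section 5 makes inclusion depend on resolution during an undefined phase. That is inconsistent with the protocol's promise of conservative imputation and with how adverse events are recorded.

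The conclusion rests on reading the SAP clause as the operative rule for missing onsets, and on taking conservative imputation to mean first dose unless the event clearly ended earlier. The first part, loss of ongoing events, does not depend on how treatment phase is read. The second, loss of events resolving shortly after treatment stops, does.

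The documents do not give the number of such events. It is probably small, and no direction or size of net bias in the safety tables can be claimed. The window end and the CTCAE version are secondary: one calls for disclosure, the other for an editorial correction.

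**What to change.** In SAP section 5:

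- Treat an adverse event with a completely missing onset as treatment-emergent unless its resolution date is before the first dose.
- Impute a partial onset date to the first-dose date whenever the known part allows it, and write the rule down.
- Define the treatment phase, or use the treatment-emergent period throughout.
- Give CTCAE 4.03 for adverse events, as in the protocol, and state the MedDRA version separately.

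In SAP section 6, declare that the treatment-emergent period now ends at new anticancer therapy. Add a supportive summary on the protocol's 30-day window, flagging events that start on or after new therapy.

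The cost is SAP wording, one changed derivation and one extra summary, all on data the protocol already collects. Reported rates may rise slightly. The rule may also take in an occasional blank-onset event that began late, which is the conservative direction.
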